## 10.1.10. Publication Policy

The full terms regarding publication of the results of this study are outlined in the applicable Clinical Study Agreement.

## 10.2. Appendix 2: Clinical Laboratory Tests

The tests detailed in Table 19 will be performed by the central laboratory.

- Protocol-specific requirements for inclusion or exclusion of participants are detailed in Section 5 of the protocol.
- Additional tests may be performed at any time during the study as determined necessary by the Investigator or required by local regulations.

**Table 19: Protocol-Required Safety Laboratory Assessments** 

Laboratory Assessments	Parameters		
Hematology	Platelet count RBC count Hemoglobin Hematocrit	RBC indices: Mean corpuscular volume Mean corpuscular hemoglobin % Reticulocytes	WBC count with differential: Neutrophils Lymphocytes Monocytes Eosinophils Basophils
Clinical chemistry	BUN Chloride Potassium Bicarbonate Sodium Glucose	AST ALT Alkaline phosphatase Gamma glutamyltransferase HbA1C (Screening only) Urea	Total and direct bilirubin Total protein Albumin Cholesterol (total) LDL HDL Triglycerides Creatinine Creatine phosphokinase
Coagulation Routine urinalysis	International normalized ratio, partial thromboplastin time, prothrombin time  Specific gravity, pH, glucose, protein, blood, ketones, bilirubin, urobilinogen, nitrite, leukocyte esterase  Microscopic examination (if any leucocytes, more than a trace protein, nitrites, and blood [if not menstruating] are abnormal)		
Other screening tests	
 
Alcohol breath and urine drug screen (to include at minimum: amphetamines, barbiturates, benzodiazepines, cocaine, opiates, phencyclidine, methamphetamine, 3,4-methylenedioxy-methamphetamine, methadone, and tetrahydrocannabinol [cannabinoids])
 
IgG, IgA and IgM concentration
 
HIV-1 and HIV-2 antibodies, HBsAg, anti-HBC IgG + IgM (if IgG positive), and anti-HCV with confirmation by HCV RNA
 
Serum hCG pregnancy test (as needed for women of childbearing potential)
 
FSH (postmenopausal females only)
 
		
IRR	• In the event of an IRR, it is recommended to collect a blood sample for assessment of tryptase, histamine, CRP, cytokines, and complement as soon as the IRR is observed (prior to administering any IRR medication), and 2 hours, 24 hours and 7 days (prior to the next dose of study drug) after onset of the IRR.		
Signs of infection	If a participant shows signs of infection, the following investigations should be included:  • Blood cultures (taken prior to start of antibiotics)  • Routine profile		

Abbreviations: ALT = alanine aminotransferase; AST = aspartate aminotransferase; BUN = blood urea nitrogen; CRP = C-reactive protein; FSH = follicle stimulating hormone; HbA1c = glycated hemoglobin; HBC = hepatitis B core antibody; HBsAg = hepatitis B surface antigen; hCG = human chorionic gonadotropin; HCV = hepatitis C virus; HDL = high-density lipoprotein; HIV = human immunodeficiency virus; Ig = immunoglobulin; IRR = infusion-related reaction; LDL = low-density lipoprotein; RBC = red blood cells; RNA = ribonucleic acid; WBC = white blood cells.

Investigators must document their review of each laboratory safety report. Laboratory/analyte results that could unblind the study will be reviewed by dedicated unblinded staff at the investigative sites or other blinded personnel until the study has been unblinded.

# 10.3. Appendix 3: Adverse Events: Definitions and Procedures for Recording, Evaluating, Follow-up, and Reporting

#### 10.3.1. Definition of AE

#### **AE Definition**

- An AE is any untoward medical occurrence in a participant or clinical investigation participant administered a pharmaceutical product and which does not necessarily have to have a causal relationship with this treatment (ICH E2A).
- Note: An AE can therefore be any unfavorable and unintended sign (including an abnormal laboratory finding), symptom, or disease (new or exacerbated) temporally associated with the use of study intervention, whether or not considered related to the study intervention.

#### **Events Meeting the AE Definition**

- Any abnormal laboratory test results (hematology, clinical chemistry, or urinalysis) or other safety assessments (eg, ECG, radiological scans, vital signs measurements).
- Exacerbation of a chronic or intermittent pre-existing condition including either an increase in frequency and/or intensity of the condition.
- New conditions detected or diagnosed after study intervention administration even though it may have been present before the start of the study.
- Signs, symptoms, or the clinical sequelae of a suspected drug-drug interaction.
- Signs, symptoms, or the clinical sequelae of a suspected overdose of either study intervention or a concomitant medication. Overdose per se will not be reported as an AE/SAE unless it is an intentional overdose taken with possible suicidal/self-harming intent. Such overdoses should be reported regardless of sequelae.

## **Events Not Meeting the AE Definition**

- Medical or surgical procedure (eg, endoscopy, appendectomy): The condition that leads to the procedure is the AE. Situations in which an untoward medical occurrence did not occur (eg, hospitalization for elective surgery if planned before the signing the ICF, admissions for social reasons or for convenience).
- Anticipated day-to-day fluctuations of pre-existing disease(s) or condition(s) present or detected at the start of the study that do not worsen.
- A medication error (including intentional misuse, abuse, and overdose of the product) or use other than what
  is defined in the protocol is not considered an AE unless there is an untoward medical occurrence as a result
  of a medication error.
- Cases of pregnancy that occur during maternal or paternal exposure to study intervention are to be reported within 24 hours of Investigator/site awareness. Data on fetal outcome and breastfeeding will be collected for regulatory reporting and safety evaluation.
- Situations in which an untoward medical occurrence did not occur (social and/or convenience admission to a hospital).

#### 10.3.2. Definition of SAE

If an event is not an AE per definition above, then it cannot be an SAE even if serious conditions are met (eg, hospitalization for signs/symptoms of the disease under study, death due to progression of disease).

#### An SAE is defined as any untoward medical occurrence that, at any dose:

#### 1. Results in death

#### 2. Is life-threatening

The term "life-threatening" in the definition of "serious" refers to an event in which the participant was at risk of death at the time of the event. It does not refer to an event, which hypothetically might have caused death, if it was more severe.

#### 3. Requires inpatient hospitalization or prolongation of existing hospitalization

- In general, hospitalization signifies that the participant has been detained (usually involving at least an overnight stay) at the hospital or emergency ward for observation and/or treatment that would not have been appropriate in the physician's office or outpatient setting. Complications that occur during hospitalization are AEs. If a complication prolongs hospitalization or fulfills any other serious criteria, the event is serious. When in doubt as to whether "hospitalization" occurred or was necessary, the AE should be considered serious
- Hospitalization for elective treatment of a pre-existing condition that did not worsen from baseline is not considered an AE.

#### 4. Results in persistent disability/incapacity

- The term disability means a substantial disruption of a person's ability to conduct normal life functions.
- This definition is not intended to include experiences of relatively minor medical significance such as uncomplicated headache, nausea, vomiting, diarrhea, influenza, and accidental trauma (eg, sprained ankle) which may interfere with or prevent everyday life functions but do not constitute a substantial disruption.

## 5. Is a congenital anomaly/birth defect

#### 6. Other situations:

- Medical or scientific judgment should be exercised in deciding whether SAE reporting is appropriate in
  other situations such as important medical events that may not be immediately life-threatening or result in
  death or hospitalization but may jeopardize the participant or may require medical or surgical intervention to
  prevent one of the other outcomes listed in the above definition. These events should usually be considered
  serious.
- Examples of such events include invasive or malignant cancers, intensive treatment in an emergency room or at home for allergic bronchospasm, blood dyscrasias or convulsions that do not result in hospitalization, or development of drug dependency or drug abuse.

## 10.3.3. Recording and Follow-Up of AE and/or SAE

#### Recording of AE and/or SAE

- When an AE/SAE occurs, it is the responsibility of the Investigator to review all documentation (eg, hospital progress notes, laboratory reports, and diagnostics reports) related to the event.
- The Investigator will then record all relevant AE/SAE information in the CRF.
- It is not acceptable for the Investigator to send photocopies of the participant's medical records to Alexion in lieu of completion of the AE/SAE CRF page.
- There may be instances when copies of medical records for certain cases are requested by Alexion. In this case, all participant identifiers, with the exception of the participant number, will be redacted on the copies of the medical records before submission to Alexion.
- The Investigator will attempt to establish a diagnosis of the event based on signs, symptoms, and/or other
  clinical information. Whenever possible, the diagnosis (not the individual signs/symptoms) will be
  documented as the AE/SAE.

#### **Assessment of Intensity**

The Investigator will make an assessment of intensity for each AE and SAE reported during the study and assign it to one of the following categories from National Cancer Institute CTCAE v5.0, published 27 Nov 2017:

- Grade 1: Mild (awareness of sign or symptom, but easily tolerated)
- Grade 2: Moderate (discomfort sufficient to cause interference with normal activities)
- Grade 3: Severe (incapacitating, with inability to perform normal activities)
- Grade 4: Life-threatening
- Grade 5: Fatal

#### Recording of AE and/or SAE

#### **Assessment of Causality**

- The Investigator is obligated to assess the relationship between the study intervention and each occurrence of each AE or SAE. An Investigator causality assessment must be provided for all AEs (both nonserious and serious). This assessment must be recorded in the CRF and on any additional forms, as appropriate. The definitions for the causality assessments are as follows:
  - Not related: There is no reasonable possibility the study intervention caused the AE.
    - The AE has a more likely alternative etiology; it may be due to underlying or concurrent illness, complications, concurrent treatments, or effects of another concurrent drug.
    - The event does not follow a reasonable temporal relationship to administration of the study intervention.
  - Related: There is a reasonable possibility the study intervention caused the AE.
    - The AE has a temporal relationship to the administration of the study intervention.
    - The event does not have a likely alternative etiology.
    - The event corresponds with the known pharmaceutical profile of the study intervention.
    - There is improvement on discontinuation and/or reappearance on rechallenge.
- The Investigator will use clinical judgment to determine the relationship.
- Alternative causes, such as underlying disease(s), concomitant therapy, and other risk factors, as well as the temporal relationship of the event to study intervention administration will be considered and investigated.
- The Investigator will also consult the IB and/or Product Information, for marketed products, in his/her assessment.
- For each AE/SAE, the Investigator **must** document in the medical notes that he/she has reviewed the AE/SAE and has provided an assessment of causality.
- There may be situations in which an SAE has occurred, and the Investigator has minimal information to include in the initial report to Alexion. However, it is very important that the Investigator always make an assessment of causality for every event before the initial transmission of the SAE data to Alexion.
- The Investigator may change his/her opinion of causality in light of follow-up information and send an SAE follow-up report with the updated causality assessment.
- The causality assessment is one of the criteria used when determining regulatory reporting requirements.

#### Follow-up of AEs and SAEs

- The Investigator is obligated to perform or arrange for the conduct of supplemental measurements and/or evaluations as medically indicated or as requested by Alexion to elucidate the nature and/or causality of the AE or SAE as fully as possible. This may include additional laboratory tests or investigations, histopathological examinations, or consultation with other health care professionals.
- If a participant dies during participation in the study or during a recognized follow-up period, the Investigator will provide Alexion with a copy of any post-mortem findings including histopathology.
- New or updated information will be recorded in the originally completed CRF.
- The Investigator will submit any updated SAE data to Alexion within 24 hours of receipt of the information.

## 10.3.4. Reporting of SAEs

## SAE Reporting to Alexion via Paper Safety Reporting Form

- All SAEs will be recorded and reported to Alexion or designee immediately and within 24 hours of awareness.
- SAEs will be reported using the Safety Reporting Form and submitted to Alexion Global Drug Safety (GDS). The Investigator must complete, sign, and date the SAE pages, verify the accuracy of the information recorded on the SAE pages with the corresponding source documents, and send a copy via email or facsimile to the contact information provided below:
  - Email: or Fax:
- Additional follow-up information, if required or available, should be entered into the CRF and sent to Alexion GDS within 24 hours of the Investigator or study site staff becoming aware of this additional information via the reporting process outlined above.
- For all SAEs, the Investigator must provide the following:
  - Appropriate and requested follow-up information in the time frame detailed above
  - Causality of the SAE(s)
  - Treatment of/intervention for the SAE(s)
  - Outcome of the SAE(s)
  - Medical records and laboratory/diagnostic information
- All paper forms and follow-up information submitted to Alexion GDS **must** be accompanied by a cover page signed by the Investigator.
- Paper source documents and/or reports should be kept in the appropriate section of the study file.

## 10.4. Appendix 4: Guidelines for Grading and Management of Allergic or Infusion-Related Reactions

Infusion-associated reactions are a potential risk with the use of monoclonal antibodies; these reactions can be nonimmune or immune mediated (eg, hypersensitivity reactions). Signs and symptoms may include headache, fever, facial flushing, pruritus, myalgia, nausea, chest tightness, dyspnea, vomiting, erythema, abdominal discomfort, diaphoresis, shivers, hypertension, lightheadedness, hypotension, palpitations, and somnolence. Signs and symptoms of hypersensitivity or allergic reactions may include hives, swollen face, eyelids, lips, or tongue, or trouble with breathing.

All infusion-associated reactions will be reported to the Investigator and qualified designee. The Investigator and qualified designee are responsible for detecting, documenting, and recording events that meet the definition of AE or SAE and remain responsible for following up events that are serious, considered related to the study drug, or study procedures; or that caused the participant to discontinue ALXN1830.

Definitions and procedures for recording, evaluating, follow-up, and reporting AEs and SAEs are outlined in Section 10.3.

Before any infusion is started, the treating physician and other appropriate personnel must make certain that medication (i.e., adrenaline, inhaled beta agonists, antihistamines, corticosteroids) and other equipment to treat anaphylaxis are readily available. The infusion must be stopped immediately if Grade  $\geq 2$  allergic/hypersensitivity reactions (including drug fever) or Grade  $\geq 3$  cytokine release syndrome/acute infusion reaction occurs. The Sponsor must be notified within 24 hours of any infusion reaction requiring interruption or discontinuation of study drug or meet the criteria of AESI.

Patients /subject who experience a reaction during the administration of study drug should be treated according to institutional guidelines. For a Grade 1 or Grade 2 infusion reaction, the infusion should be temporarily stopped and treatment with an antihistamine (eg, diphenhydramine 25 to 50 mg orally or equivalent) and acetaminophen (650 mg orally or equivalent) may be considered. If the patient's signs and symptoms have resolved (with or without administration of the above medication), the infusion may be restarted. However, the patients should be infused at a slower rate and be monitored closely for any signs and symptoms of infusion reactions during the remainder of the infusion. Patients experiencing an infusion reaction should be observed in the clinic until resolution of the reaction, or until the Investigator determines the patient is no longer at risk. Patients who experience a severe reaction during administration of study drug resulting in discontinuation of study drug should undergo all scheduled safety, PK, and PD evaluations required by the protocol.

If anaphylaxis occurs according to the criteria listed below, then administration of subcutaneous epinephrine (1/1000, 0.3 mL to 0.5 mL, or equivalent) should be considered. In the case of bronchospasm, treatment with an inhaled beta agonist also should be considered. Patients administered an antihistamine for the treatment or prevention of an infusion reaction should be given appropriate warnings about drowsiness and impairment of driving ability before being discharged from the center.

In the event of an IRR considered to be a hypersensitivity reaction, it is recommended to collect a blood sample for assessment of tryptase, histamine, CRP, and complement as soon as the IRR is observed (prior to administering any IRR medication), 2 hours after onset of the IRR, and 7 days later, prior to the next dose of study drug.

Table 20: Grading and Management of Allergic or Infusion-Related Reactions

Adverse	Grade					
Event	1	2	3	4	5	
Infusion-related reaction	Mild transient reaction; infusion interruption not indicated; intervention not indicated	Therapy or infusion interruption indicated but responds promptly to symptomatic treatment (eg, antihistamines, non-steroidal anti-inflammatory drugs [NSAIDs], narcotics, IV fluids): prophylactic medications indicated for ≤ 24 hours	Prolonged (eg, not rapidly responsive to symptomatic medication and/or brief interruption of infusion); recurrence of symptoms following initial improvement, hospitalization indicated for clinical sequelae	Life-threatening consequences; urgent intervention required	Death	
Allergic reaction	Transient flushing or rash, drug fever < 38.0°C. Intervention not indicated	Therapy or infusion interruption indicated but responds promptly to symptomatic treatment (eg, antihistamines, NSAIDs, narcotics, IV fluids): prophylactic medications indicated for ≤ 24 hours	Prolonged (eg, not rapidly responsive to symptomatic medication and/or brief interruption of infusion); recurrence of symptoms following initial improvement, hospitalization indicated for clinical sequelae (eg, renal impairment, pulmonary infiltrates)	Life-threatening consequences; urgent intervention required	Death	
Anaphylaxis	-	_	Symptomatic bronchospasm, with or without urticarial; parenteral intervention indicated; allergy-related edema/angioedema; hypotension	Life-threatening consequences; urgent intervention required	Death	
Cytokine release syndrome	Mild reaction; infusion interruption not indicated; intervention not indicated	Therapy or infusion interruption indicated but responds promptly to symptomatic treatment (eg, antihistamines, NSAIDs, narcotics, IV fluids): prophylactic medications indicated for ≤ 24 hours	Prolonged (eg, not rapidly responsive to symptomatic medication and/or brief interruption of infusion); recurrence of symptoms following initial improvement, hospitalization indicated for clinical sequelae (eg, renal impairment, pulmonary infiltrates)	Life-threatening consequences; pressor or ventilator support indicated	Death	

Abstracted from NCI CTCAE Version 5.0.

Abbreviations: IV = intravenous; NSAIDs = nonsteroidal anti-inflammatory drugs

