# 7.2.2. Safety Stopping Rules (Individual, Cohort and Study Level Stopping Rules) Individual Level:

- Study drug will be discontinued immediately (if applicable) and permanently if any of the following occurs:
  - Development of a 'serious' adverse reaction (AR), or 'severe' (≥ Grade 3) AR.
  - Development of a 'serious' adverse reaction (AR), or 'severe' (≥ Grade 3) IRR.
- If a moderate Grade 2 AR is observed, study drug administration may be continued, delayed, or discontinued in accordance with Investigator's clinical judgment and in consultation with Alexion.

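### Section 10.4 pauses the infusion for Grade 1 reactions that Table 20 defines as not needing interruption, and does not settle whether a Grade 2 hypersensitivity reaction permits restart

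*Protocol*

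**What the plan says.** Protocol Section 10.4 holds both narrative instructions and a grading table.

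- The narrative says "For a Grade 1 or Grade 2 infusion reaction, the infusion should be temporarily stopped", adds that an antihistamine and acetaminophen may be considered, and says that once signs and symptoms have resolved "the infusion may be restarted", at a slower rate.
- An earlier paragraph of the same section begins "The infusion must be stopped immediately if Grade". The threshold that follows is Grade 2 or higher for allergic or hypersensitivity reactions, and Grade 3 or higher for cytokine release syndrome or acute infusion reaction. Nothing is said there about restarting.
- Table 20, whose title covers both grading and management, defines Grade 1 infusion-related reaction as "Mild transient reaction; infusion interruption not indicated; intervention not indicated" and Grade 1 cytokine release syndrome as "Mild reaction; infusion interruption not indicated; intervention not indicated". Grade 1 allergic reaction reads "Transient flushing or rash, drug fever < 38.0°C. Intervention not indicated".
- For all three of these reaction types, Grade 2 opens with "Therapy or infusion interruption indicated but responds promptly to symptomatic treatment".

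Protocol Section 7.2.2 adds a general provision: "If a moderate Grade 2 AR is observed, study drug administration may be continued, delayed, or discontinued", by investigator judgment and in consultation with the sponsor.

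**The concern.** Table 20 uses the need for therapy or interruption to separate Grade 1 from Grade 2. If the text directs a pause at Grade 1, the infusion record of a Grade 1 reaction shows an event that the table associates with Grade 2. A rater is not told whether that pause counts. Two raters could then grade the same reaction differently while each follows the protocol.

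The second difficulty concerns handling. Staff facing a Grade 2 hypersensitivity reaction can find one paragraph that is silent on restart and another that allows it, with nothing to say which governs.

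Safety is the primary objective and is reported by grade, so consistent grading matters even in a descriptive study.

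**Working it through.** The plan gives no figure to reproduce on this point. The check sets the passages side by side.

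**Step 1: Grade 1, row by row.** Table 20 has four rows. Anaphylaxis has no Grade 1 or Grade 2 entry, which leaves three.

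| Table 20 row | Grade 1 definition | Against the narrative's pause at Grade 1 |
|---|---|---|
| Infusion-related reaction | "Mild transient reaction; infusion interruption not indicated; intervention not indicated" | Direct conflict on interruption |
| Cytokine release syndrome | "Mild reaction; infusion interruption not indicated; intervention not indicated" | Direct conflict on interruption |
| Allergic reaction | "Transient flushing or rash, drug fever < 38.0°C. Intervention not indicated" | Interruption not mentioned; tension only with the statement on intervention |

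The interruption conflict is therefore direct in 2 of 3 rows. The tension over medication is weaker in every row, because the narrative only allows medication to be considered.

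**Step 2: why this reaches the grade.** The Grade 2 entry in all three rows turns on therapy or interruption being indicated. Protocol Section 10.3.3 (Assessment of Intensity) describes Grades 1 and 2 by symptoms instead: easily tolerated, against interfering with normal activities. A well-tolerated reaction that is paused under the narrative is Grade 1 by Section 10.3.3. Under Table 20 it can be read as Grade 2 by anyone who takes the directed pause as an indicated one. No sentence tells the rater which reading to use.

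**Step 3: Grade 2 hypersensitivity.** Two rules apply to one event if hypersensitivity counts as an infusion reaction. Three places say that it does. Section 10.4 opens by giving hypersensitivity as an example of an immune-mediated infusion reaction. It later refers to infusion-related reactions that are considered hypersensitivity reactions. Section 8.3.5.1 includes both immune and non-immune reactions in the term.

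- Rule A (immediate stop): applies from Grade 2 for hypersensitivity; restart not addressed.
- Rule B (temporary stop): applies to a Grade 2 infusion reaction; restart allowed after resolution.

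Both rules stop the infusion. The unanswered question is restart.

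**Step 4: where the inconsistency lands.**

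- SAP Section 12.1 tabulates treatment-emergent events by toxicity grade and by maximum toxicity grade. Affected.
- SAP Section 8.7 summarises the number of infusion interruptions. Affected, since a directed Grade 1 pause may add to the count.
- Protocol Section 10.4 requires sponsor notice within 24 hours of any infusion reaction requiring interruption. Affected, since a directed Grade 1 pause may qualify.
- Protocol Section 8.3.5 makes an infusion reaction one of special interest at Grade 3 or higher, or when it may jeopardise the participant and needs immediate intervention. A shift from Grade 1 to Grade 2 does not reach this. The only Grade 2 threshold there is for delayed hypersensitivity.
- The cohort rule on Grade 2 adverse reactions in Protocol Section 7.2.2 needs 2 participants whose reaction has not improved by 14 days. A transient reaction graded one step too high would not ordinarily meet it.
- The cohort rule on infusion reactions refers back to the individual-level criterion, which is serious or Grade 3 and above. Not reached.

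**Step 5: size of one reclassification.** In a full cohort with 6 active participants, moving one participant from Grade 1 to Grade 2 changes the Grade 2 rate by 1/6 = 0.167, or about 17 percentage points. This shows how sensitive the table is; it does not estimate how often misgrading would occur. It does not apply to Cohort 2, which has only 2 participants in total (SAP Section 4.1).

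**The case against.** The best defence is that the table grades and the text manages. Table 20 is abstracted from CTCAE Version 5.0, where a statement that interruption is not indicated describes clinical need and does not forbid a cautious pause. The narrative assigns the grade first and pauses second, and nowhere says that a pause raises the grade. Section 10.3.3 already offers symptom-based descriptions. This has force: a reader might infer that handling determines grade under this protocol, and the documents do not go that far. What stands is that the table presents itself as covering management as well as grading, its Grade 1 and Grade 2 entries turn on the very action the text directs, and no sentence tells the rater to set a directed pause aside.

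On Grade 2, a reader might infer that the two rules send participants in opposite directions. They do not. Both stop the infusion, and the immediate-stop rule is not called permanent, whereas Section 7.2.2 states permanence expressly where it intends it. It can also be argued that allergic and infusion reactions are separate classes, since the immediate-stop sentence and Table 20 give them separate thresholds or rows. The three places that count hypersensitivity among infusion reactions prevent that from resolving the overlap.

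Section 7.2.2 might look like a third, competing rule. It gives general discretion over any Grade 2 adverse reaction and can coexist with either rule. It needs a cross-reference and is not itself a contradiction.

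**Conclusion.** The point holds as an internal inconsistency in Section 10.4. The Grade 1 part is a direct conflict on interruption for infusion-related reaction and cytokine release syndrome. The Grade 2 part is an unresolved overlap confined to restart, and it rests on reading infusion reaction to include hypersensitivity, as Sections 8.3.5.1 and 10.4 do.

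The consequence is limited to consistency of handling, Grade 1 versus Grade 2 assignment in descriptive tables, the interruption count and the 24-hour notice. SAP Section 12 plans no inferential safety analysis, so no test is affected.

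Two stronger readings should be set aside. One is that the special-interest definition for infusion reactions or the cohort stopping rules would be materially affected; their thresholds, set out in Step 4, rule that out. The other is that every infusion reaction seen with this drug so far lay in the mild-to-moderate range where the rules conflict. Protocol Section 2.3.3 says this of the reactions at multiple intravenous doses of 20 mg/kg, while Table 13 reports 6 reactions across clinical studies without grades.

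The study ended early (SAP Section 4.1), so what remains to be gained is clear reporting of grades here and a sound text if the appendix is used again.

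**What to change.** Reconcile the immediate-stop paragraph, the temporary-stop paragraph and Table 20 in Section 10.4, with a cross-reference to Section 7.2.2, so that each grade and reaction type carries one instruction, including whether restart is allowed. Which instruction is right is a clinical decision on which this review takes no view.

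Also state how an infusion pause made under the protocol is treated when the grade is assigned, so that the handling does not by itself determine the grade. That sentence is useful however the Grade 1 instruction is settled.

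For data already collected, the study report should say how reactions with a pause were graded, so that the grade tables and the interruption count can be read together.

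The cost is protocol wording, one line in the adverse event completion guideline and a sentence in the report. No visit, sample or analysis changes.
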